### 6.3 Study Procedure

[figure not shown]
During the study procedure, subjects will be treated with the CLEAR + BRILLIANT TOUCH® diode laser device combination wavelength 1440-nm and 1927-nm treatment.

Perform pattern preview test prior to use of device.

- 1. First the face will be cleansed with alcohol, topical anesthetic of 7% Lidocaine/7% Tetracaine will be applied 30 minutes prior to treatment.
- 2. Prior to treatment, the anesthetic will be fully wiped off and then face is cleaned again with rubbing alcohol to ensure face is free of all moisture and water. Allow to dry.
- 3. Provide patient protective eyewear. (Disposable or Non-disposable laser eye shields). Laser goggles for staff. With appropriate protection range for the system laser wavelengths (1440 nm  $\pm$  20 nm and 1927  $\pm$  20 nm) and optical density of 5 or greater.
- 4. Attach single-use treatment tip.
- 5. Pre-set for 3200 cm^2 treatment area coverage or Time: 40 minutes.
- 6. Full face will be treated with 4 passes of the 1440-nm Original handpiece on high setting for all skin types I-VI, with two passes in the horizontal direction and two passes in the vertical direction (Fig A.) in each treatment zone (Fig B, C). (Adjustments may be made to lower setting for patient tolerance)

7. Full face will be treated with 4 passes of the 1927-nm Perméa on high setting for all skin types I-VI, with two passes in the horizontal direction and two passes in

- the vertical direction in each treatment zone. (Adjustments may be made to lower setting for patient tolerance)
- 8. The total is a combined 8 passes in each treatment zone.
- 9. CeraVe® moisturizer and SPF 30+ to be applied to entire face immediately after treatment.

#### 6.4 Follow-up Procedure

Following the procedure, the research staff and the subject will care for the treated area using the Post-Procedure Care Guidelines listed below:

#### **Post Care and Instructions:**

- 1. Wash face with CeraVe® gentle cleansing product only.
- 2. Do not use an abrasive cleanser or brush device to clean face.
- 3. Apply CeraVe® moisturizer minimum twice a day while skin is healing and then as needed.
- 4. SPF 30+ daily. (approved by investigator)

  Sun exposure before and during treatment can increase the risk of unwanted pigmentation. After treatment the skin is more sensitive to the sun, which can increase the risk of unwanted pigmentation and sunburn. Post-treatment individuals should plan to use a high SPF sunscreen on a regular basis whenever they are outside. Ideally, a dual UVA/UVB sunscreen should be applied containing both a physical sun block (either or both zinc oxide or titanium dioxide) with a sun protection factor of 30 or above. Applying sunscreen helps maintain good results. In general, it is recommended that direct sunlight is avoided and to wear sun-protective clothing (i.e. a wide-brimmed hat) when possible.
- 5. Schedule next appointment.
- 6. Review and dispense the Subject home diary for post treatment skin effects.
- 7. For patients on the 8% hydroquinone therapy (Skin types IV-VI) hold this application while skin is healing, then restart QHS or as directed.

Subjects will be asked to return to the study site for subsequent procedures and post treatment follow up.

Post procedure Standard 2D images will be captured via the Canfield Scientific Inc, VISIA CA imaging system during the follow-up visits.

#### 6.5 Data Collection

Subject demographic information, procedural data, adverse events, treatment observations and study required assessments will be documented on the case report forms (CRFs). Study subjects will complete satisfaction and modified global aesthetic improvement scale evaluations at the 3-month follow up. The Investigators will assess post treatment skin effects immediately post treatment, at follow up visits (prolonged post treatment) and quartile improvement scores at one (1) month and three (3) months in comparison to baseline photography. Blinded Investigators will provide analysis of unmarked 2D photo sets via Canfield clinical system. Reviewers will select the order of baseline and post treatment at one (1) month and three (3) months. Then based on their selection assess photos for

percentage improvement in photoaging damage using the quartile improvement scale and score 0-4.

### 6.5.1 Photography

VISIA CA facial photography system and services will be provided by the photography vendor, Canfield Scientific, Inc. (Parsippany, NJ) to document treatment effect from baseline to follow up visits. The camera system standardizes the facial (front, left and right oblique) images captured and lighting modalities.

All consenting subjects' study photographs will be captured using the equipment, supplies, and guidelines provided by Canfield to have consistent visual representation of the facial appearance during the study treatment.

Images will be captured, viewed, and uploaded using Canfield Clinical Services website which automatically checks, sums, encrypts, packages, and transfers the data to a secure, validated and compliant web server hosted by Canfield. Only approved individuals by the Sponsor have access to the study database on the website.

Detailed instructions for all aspects of the photography procedures will be supplied separately in the investigator user manual to be provided by Canfield. Images will be utilized for study research purposes (add other purposes, analysis if applicable).

#### 6.5.2 Specimens

Five patients who provide additional consent to provide biopsies will have three (3) punch biopsies taken by the Investigator or site designee in the treatment area (area of photodamage). Location of biopsies will be pre-auricular, at temporal hairline, or the forearm. Pre- and post-treatment biopsies must be taken from the same general location for each patient.

- The first biopsy will be collected at Screening/Baseline visit (pre-Treatment #1)
   The first treatment will be subsequently scheduled at the discretion of the principal investigator as they determine the biopsy site to be healed for treatment
- The second biopsy will be collected at 14 days following the first treatment.
   The second treatment will be subsequently scheduled at the discretion of the principal investigator as they determine the biopsy site to be healed for treatment.
- The third biopsy will be collected at 3-month follow up (3-months post final treatment, Treatment #4).

#### 6.6 Final Study Visit

Three-month 2D follow-up photographs will be taken captured via the Canfield Scientific Inc, VISIA CA imaging system.

Subjects will complete satisfaction surveys and GAIS overall improvement scores.

Investigators will complete Quartile Improvement Scales comparing baseline photography to 3 months photography.

### 6.7 Study Completion

The Sponsor or its representative will notify the Investigator and/or the IRB, as applicable, to inform them when the study is complete. The study will be considered complete when all enrolled subjects either have completed study visits through Visit 7 (3-month follow up) or have been discontinued from the study prior to Visit 7 for any reason.

#### 6.8 Schedule of Events Table

	VISIT 1	VISIT 2	VISIT 2a	VISIT 3	VISIT 4	VISIT 5	VISIT 6	VISIT 7
PROCEDURES	Screening Visit (Day -30 to 0)	Treatment #1 (Baseline)	Day 14 Biopsy (14 days post treatment #1, +/- 7 days)	Treatment #2 (1-month post treatment #1, +/- 7 days)	Treatment #3 (1-month post treatment #2, +/- 7 days)	Treatment #4 (1-month post treatment #3, +/- 7 days)	1-Month F/U (1 month post final treatment, +/- 7 days)	3-Month F/U (3 months post final treatment, +/- 7 days)
Informed Consent/Photo	X							
Release								
Demographics	X							
Medical History	X	X						
Vital Signs	X							
Concomitant Medications	X	X		X	X	X	Х	X
Inclusion/Exclusion Criteria	Х	Х						
Previous Therapies	Х	Х						
Urine Pregnancy Test	X	X						
2D Standard Photography		X		X	Х	Х	X	Х
Investigator Intake Assessments	Х	X				, , , , , , , , , , , , , , , , , , ,	, A	
Punch Biopsy	X		X					X
Laser Treatment		X		X	Х	Х		
VAS Visual Analog Scale		X		X	X	X		
Side Effects Evaluation		X		X	X	X	Х	Х
Adverse Events Review	Х	X		X	X	X	X	X
Investigator Quartile Improvement Evaluation							X	X
Prolonged Treatment Effects							Х	Х
Subject GAIS								Х
Subject Diary a		X		X	Х	Х		
Subject Satisfaction		,				,		Х
End of Treatment(s)						Х	1	,,
- · · · · · · · · · · · · · · · · ·		1			1	, ,	1	

<sup>a. Subject's will log post-treatment skin responses, side effects (e.g., erythema, edema) using a scale of 0 to 3 (none to marked) after each treatment for seven (7) days in the subject diary.

#### Visit 1 (Day 0-30)

Screening

A prospective subject is to be examined to determine if they qualify for entry into the study. This initial examination will include:

- Obtain written Informed Consent and photographic release
- Review Inclusion/Exclusion Criteria
- Record Medical History/Meds/Vital Signs
- Urine Pregnancy Test (if applicable): only one is necessary prior to start of treatments.
- Dispense CeraVe® Products
- Skin types IV-VI: Begin Hydroquinone 8% QHS at discretion of treating physician 2-3 weeks prior to first treatment. Hold while skin is healing, then restart QHS or as directed.
- Investigator Assessments: Glogau Photodamage, Fitzpatrick Skin Type and Wrinkle & Elastosis Scale
- Biopsy #1 of five patients (baseline)

Note: Screening and Baseline visits may occur on the same day for non biopsy patients.

#### Visit 2

Baseline/Treatment #1 (Screening/Baseline may be on same day)

This treatment visit will include:

- Photographs prior to treatment: wait at least 15 min indoors, 2D standard photography captured via Canfield VISIA CA.
- Urine Pregnancy Test (if applicable): only one is necessary prior to start of treatments.
- · Laser treatment to the face
- VAS Scale
- Post Treatment Skin effects (provider)
- Review for Adverse Events (provider)
- Subject Diary post treatment (7 days) given to patient.

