# 1. STUDY SYNOPSIS

Name of Sponsor/Company	Bausch Health Americas, Inc.			
Name of Device	CLEAR + BRILLIANT TOUCH® diode laser 1440-nm and 1927-nm			
Title of Study	A Prospective, Single-Center Study Evaluating the Safety and Effectiveness of the CLEAR + BRILLIANT TOUCH® diode laser 1440-nm and 1927-nm Combination Wavelength Treatment.			
Number of Clinical Centers	Single Center			
Study Design	This is a prospective study of up to 30 subjects designed to assess the safety and effectiveness of a non-ablative fractional laser combination wavelength treatment for general resurfacing of photoaged skin. All study subjects will be treated on the whole face with the CLEAR + BRILLIANT TOUCH® 1440-nm and 1927-nm handpieces. Subjects will be treated with a consecutive series of four (4) treatments spaced 1 month apart, along with follow-up study visits at one (1) and three (3) months after final treatment.			
Study Population	To be eligible for the study, the subjects must have mild (I) to moderate (II) photoaging by Glogau Photodamage Scale, no more than fine wrinkles and mild elastosis by Fitzpatrick Wrinkle and Elastosis Scale (Class I-II, Score 1-6). Both males and females will be considered, between the ages 18 and 65 years and Fitzpatrick skin Types I-VI with 70% skin types I-III and 30% skin types IV-VI.  Number of subjects: Up to 30 subjects who meet all study inclusion/exclusion criteria will be considered for entry.			
Study Objective	The objective is to evaluate the effectiveness and safety of the CLEAR + BRILLIANT TOUCH® diode laser combination treatment of 1440-nm and 1927-nm.			
Study Endpoints	Primary Effectiveness Endpoint: improvement in the appearance of at least one measurement of photoaging damage (fine wrinkles, skin texture, dyschromia/pigment, skin radiance, pore size or overall appearance) by the investigator using the quartile improvement score comparing standard 2D baseline photograph captured via Canfield VISIA CA system and the 3 months post final treatment photograph. Reported percent change in improvement.			

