### 5.5 Strategies for Recruitment and Retention

The recruitment process planned for this study will include any of the following scenarios:

- An individual voluntarily schedules an appointment at the physician's office (that in the context of this study also functions as the investigator's test site) relating to the treatment of photoaging.
- The study population may also be drawn from the investigator's existing database of subjects who have expressed an interest in treatment of photoaging.
- During the visit, if the physician perceives the subject may satisfy the study qualification criteria, the physician will present to the subject the option of being a subject in the study.
- If the subject is interested in possibly taking part in the study, the physician now in the role of study investigator will personally review the informed consent form with the individual and answer any questions. The individual may sign the informed consent form at that visit or he or she may think about it for a while and sign the informed consent form later. No timeline may be set for the subject to sign the consent form. Furthermore, the subject can refuse to participate in the study.
- An individual who decides to sign the consent form and proceed with participation in the study will receive a subject ID and proceed to the study qualification phase.
- Treatment will include a screening visit, four treatment visits and two follow up visits; a total of seven office visits to complete participation. (Screening visit and first treatment may be on same day if no biopsy is taken.) Biopsy patients will have a total of eight office visits to include an additional biopsy collection at 14 days post treatment #1 for enrollment completion.

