### 5.6 Subject Enrollment

A subject is considered enrolled in the study at the time of the first treatment (Treatment #1) following confirmation of eligibility according to inclusion/exclusion criteria at the Screening Visit and again at Visit 2 (Treatment #1).

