### 6.2 Pre-Procedure

Study subjects will have verification of eligibility criteria, a brief general examination including medical history, vital signs and pre-procedure assessments as detailed below, completed within 30 days prior to undergoing the study procedure. Up to two urine pregnancy tests must be obtained prior to study procedure for females with childbearing potential (one at pre-procedure screening and one on the day of the procedure prior to the procedure if the pre-procedure screening and procedure are not performed on the same day).

The following pretreatment assessments will be performed:

- Standard 2D photographic images will be captured via the Canfield Scientific Inc, VISIA CA imaging system. The same standardized photography views (right, left, front facing) will be used throughout the study as documented in the image capture document developed for the study.
- Urine pregnancy test for females of childbearing potential; any premenopausal female capable of becoming pregnant. (Excluded: Non-childbearing potential, i.e. post-menopause, bilateral tubal ligation, oophorectomy, hysterectomy)
- Abbreviated general physical exam including medical history, vital signs, collection of subject's demographic information, Glogau photodamage assessment, Fitzpatrick skin type, Fitzpatrick Wrinkle and Elastosis Scale. (Appendixes A, B, C respectively)

Medications the subject is taking upon entry into the study should also be documented in the case report forms. Documentation should include medications that study subjects take on an elective basis in addition to prescribed medications.

After confirming fulfillment of all inclusion and exclusion criteria, the subject will be scheduled to undergo a CLEAR + BRILLIANT TOUCH® 1440-nm and 1927-nm combination wavelength treatment.

Patient Pre-treatment instructions:

[figure not shown]
- Skin types IV-VI: Begin Hydroquinone 8% QHS at discretion of treating physician, 2-3 weeks prior to first treatment. Hold while skin is healing between treatments, then restart QHS or as directed.
- Wash face with CeraVe® cleanser.
- Do not apply any topical facial products the morning of your treatment.
- Do not wear jewelry.
- Hair pulled back.
- Bring a hat to wear that shields from the sun.
- Bring on day of treatment the sponsor provided CeraVe® moisturizer and SPF to apply after treatment.

[figure not shown]

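### The Visit 1 and Visit 2 lists waive the pregnancy test that Section 6.2 requires on the day of Treatment #1 when screening was on a different day

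*Combined protocol and SAP*

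**What the plan says.** Three places in the protocol deal with pregnancy testing before Treatment #1.

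- **Section 6.2 (Pre-Procedure)** makes testing mandatory for women of childbearing potential. One test is done at screening, and there is "one on the day of the procedure prior to the procedure if the pre-procedure screening and procedure are not performed on the same day". The same section has the pre-procedure assessments "completed within 30 days prior to undergoing the study procedure".
- **Section 6.8, Schedule of Events table**, has a row "Urine Pregnancy Test" marked at Visit 1 and at Visit 2. It has no footnote or condition, and no mark at any later visit.
- **Section 6.8, visit lists**, name the test under Visit 1 and again under Visit 2. Both times they add that "only one is necessary prior to start of treatments".

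Several other provisions bear on the point. Pregnancy is exclusion criterion 1 (Section 5.4). Section 5.6 has eligibility confirmed at screening and again at Visit 2 before a subject counts as enrolled. Section 5.5 allows same-day visits only for some subjects: "Screening visit and first treatment may be on same day if no biopsy is taken". For skin types IV-VI, the Visit 1 list says "Begin Hydroquinone 8% QHS at discretion of treating physician 2-3 weeks prior to first treatment".

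**The concern.** The line in the visit lists carries no same-day condition. Read as it stands, it covers a subject screened weeks before Treatment #1, and for her it removes the need for a test that Section 6.2 makes compulsory. The visit lists are the step-by-step instructions for each visit, so a site could follow them in good faith and still depart from Section 6.2. Section 14.3 counts any non-conformance with the protocol as a deviation and allows no waivers.

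At stake are subject safety and a clean eligibility check. The Visit 2 reconfirmation of the pregnancy exclusion could rest on the screening result alone. Visit 2 is also the last scheduled test before a course of four treatments. If it is skipped, the screening test is the only one in the study. A pregnancy found before Treatment #1 is a screen failure (Section 5.7). One recognized afterwards leads to discontinuation of an enrolled subject, who is not replaced (Section 5.9.1).

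**Working it through.** The protocol gives no figure to reproduce here. The check compares the texts and then uses simple arithmetic for scale.

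**Step 1. Tests required before Treatment #1, by source**

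| Timing | Section 6.2 | Schedule of Events | Visit 1 and Visit 2 lists |
|---|---|---|---|
| Screening and Treatment #1 on the same day | 1 | marked at both visits, which coincide | 1 |
| Screening and Treatment #1 on different days | 2 | 2 | 1 |

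Section 6.2 and the visit lists agree in the same-day case. The conflict is confined to different days, where the visit lists are the outlier.

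**Step 2. Do different days arise under the protocol?** Yes, in three ways.

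- Biopsy subjects cannot use the same-day option (Section 5.5 and the note under Visit 1). Section 6.5.2 delays their first treatment until the biopsy site is judged healed.
- Subjects of skin types IV-VI who are put on hydroquinone start it 2-3 weeks before Treatment #1.
- Any other subject may be screened on a separate day, because the same-day visit is only an option.

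**Step 3. Age of a screening-only test at Treatment #1**

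- In general it is at most 30 days (Section 6.2, and the Visit 1 column of the schedule).
- If hydroquinone starts at Visit 1, it is 2 × 7 = 14 to 3 × 7 = 21 days.
- If hydroquinone starts after Visit 1, the minimum is still 14 days and the limit is the 30-day window.

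**Step 4. Subjects with separate days by protocol instruction**

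- Biopsy subjects: up to 5 (Section 7.3).
- Skin types IV-VI: the synopsis plans "70% skin types I-III and 30% skin types IV-VI", so at full enrollment 0.30 × 30 = 9. Hydroquinone is at the physician's discretion, so between 0 and 9 of them have the lead-in.
- Combined, with five biopsy subjects: 9 + 5 = 14 of 30 if all 9 receive hydroquinone and the groups do not overlap; 9 if all 9 receive it and the biopsy subjects are among them; 5 if nobody receives it.

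The figure of 14 counts only those whom the protocol itself sends to separate days. It does not cap the number exposed to the conflict, because of the third group in Step 2. The documents do not say how many subjects are of childbearing potential, so no number affected can be derived.

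**The case against.** The strongest reply is that the line is shorthand for the same-day case. The Visit 1 list ends with a note that screening and baseline may share a day for non-biopsy subjects, and the Visit 2 heading repeats the option. The Visit 2 list still names the test, which would serve little purpose if a screening test always sufficed. Section 6.2 speaks of up to two tests and states the condition in full, so on this reading the lists merely abbreviate it.

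That may well be what was intended, but the line does not say so. It also appears under Visit 1, in a list that itself provides for biopsy subjects, who are never same-day, and for a hydroquinone lead-in of 2-3 weeks. A list that expects separate days and still calls one test enough cannot be confined to the same-day case by context alone.

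Much of the rest of the reply stands. The line does not forbid a second test, and a site that follows Section 6.2 and the schedule complies with every section. Harm requires a site to rely on the visit list over two other places. The 9 treats the synopsis percentage as exact at full enrollment and assumes hydroquinone for everyone in that group; the inclusion criteria set no skin-type quota. The figure of 30 days is the firmer measure of size.

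**Conclusion.** The inconsistency is real and minor. When screening and Treatment #1 are on different days, Section 6.2 and the schedule require two tests and the visit lists say one is enough. Section 6.2 is explicit and mandatory and the schedule supports it, so it is clear which rule should govern. A site following the lists could treat on a result up to 30 days old, with no further test scheduled during the treatment course.

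The protocol's own instructions create separate days for at most 14 of 30 subjects. That assumes full enrollment, the synopsis skin-type split, hydroquinone for all of types IV-VI, five biopsy subjects and no overlap between the groups. Others may be screened on a separate day as well. The number actually affected cannot be stated. Endpoints, analysis populations and inference are not touched.

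**What to change.** Replace the line under both Visit 1 and Visit 2 in Section 6.8 with wording such as: *one test if screening and Treatment #1 are on the same day; otherwise test at screening and repeat on the day of Treatment #1 before treatment.* Leave Section 6.2 and the Schedule of Events table as they are.

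The cost is one line of wording in two places. No visit, test or procedure is added, because Section 6.2 and the schedule already call for the second test.

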#### Visit 2a

Biopsy Patients Only (14 days post treatment #1, +/- 7 days)

Biopsy #2 of selected five patients

#### Visit 3

Treatment #2

(one-month post treatment #1, +/- 7 days)

This treatment visit will include:

- Prior to treatment: wait at least 15 min indoors, 2D standard photography via Canfield VISIA CA
- · Laser treatment to the face
- VAS Scale
- Post Treatment Skin effects (provider)
- Review for Adverse Events (provider)
- Subject Diary post treatment (7 days) given to patient

#### Visit 4

Treatment #3 (one -month post treatment #2, +/- 7 days)

This treatment visit will include:

- Prior to treatment: wait at least 15 min indoors, 2D standard photography via Canfield VISIA CA
- Laser treatment to the face
- VAS Scale
- Post Treatment Skin effects (provider)
- Review for Adverse Events (provider)
- Subject Diary post treatment (7 days) given to patient

#### Visit 5

Treatment #4 (one-month post treatment #3,+/- 7 days,)

This treatment visit will include:

• Prior to treatment: wait at least 15 min indoors, 2D standard photography via Canfield VISIA CA

Page 24 of 49

- Laser treatment to the face
- VAS Scale
- Post Treatment Skin effects (provider)
- Review for Adverse Events (provider)
- Subject Diary post treatment (7 days) given to patient

#### Visit 6

Follow-Up Visit (one-month post treatment #4, +/- 7 days)

This follow-up examination will include:

- Photography: wait at least 15 min indoors, 2D standard photography via Canfield VISIA CA
- Prolonged Post Treatment Skin effects
- Review for Adverse Events
- Investigator Quartile Percent Improvement Evaluation

#### Visit 7

Follow-Up Visit (three months post treatment #4, +/- 7 days)

This follow-up examination will include:

- Photography: wait at least 15 min indoors, 2D standard photography via Canfield VISIA CA
- Prolonged Post Treatment Skin effects
- Review for Adverse Events
- Subject GAIS and satisfaction
- Investigator Quartile Percent Improvement Evaluation
- Biopsy #3 of selected five patients

